6.7 Imbalance at baseline

If randomisation has been successful, both treatment and control groups should be equivalent at baseline. As such, any imbalance will have occurred by chance. To check for and monitor imbalance, we will produce a table of descriptive characteristics for all young people who have completed a baseline questionnaire. We will also produce an equivalent table for those who have completed a T2 questionnaire to check whether any attrition experienced throughout the trial may have introduced an imbalance. These descriptive characteristics will include age, sex, ethnicity (collected by Cerridwen colleagues) and the relevant outcomes collected through questionnaires (SRDS Volume Score, BES score, SDQ externalising behaviours and prosocial scale scores, SSRS score). Categorical data will be summarised by numbers and percentages. Continuous data will be summarised by mean (SD) if data are normal and median [IQR] if data are skewed.

Depending on the quality and completeness of data received, we may also include other data collected being collected by the Cerridwen team (i.e. involvement with other services, special educational needs and disabilities (SEND) data, and English as an Additional Language (EAL) status).

We will present a cross-tabulation of counts and percentages for each category above against allocation group. For continuous variables, we will present the means and standard deviation. This analysis will be used to inform our understanding of the extent to which our initial sample was balanced across the two groups, and whether any attrition experienced throughout the trial has introduced an imbalance. We will discuss any differences and their implications in the final report.

6.8 Missing data

Throughout the trial, the evaluation team will work closely with the Cerridwen intervention team to support the collection of high quality and complete data for all young people. However, missing data may arise due to either item non-completion or sample attrition (i.e. young people who do not complete all items of the baseline or the T2 questionnaires). We will assess both the extent of missingness and patterns of missingness in the data. In line with YEF guidance (2021a) we will report on both: (1) the proportion of missing data in the trial, and (2) the extent and pattern of missingness in the data. This will involve analysis of whether data is missing completely at random (MCAR), missing at random (MAR), or missing not at random (MNAR). MCAR and MAR mean that complete cases are unlikely to be biased subsequent to adjustment but may be underpowered, while MNAR suggests that structural bias has been introduced to the sample.

We will attempt to establish the missing mechanism (i.e. which variables in the data are predictive of non-response) through logistic regression models. This will model the presence of missing outcomes data with additional information that may be predictive of missingness. We will conduct this analysis in line with the flow chart in Figure 1 in the YEF analysis guidance (2021a). This outlines the following approach:

- If the prevalence of missing data is less than 5%, no further action is required as complete case analysis is unlikely to be biased.
- If outcomes data is MAR conditional on co-variates, we will include these co-variates in our primary analysis model and discuss the implications in full.
- If a covariate is MAR conditional on other covariates, we will conduct multiple imputation (MI). Treatment effects from the MI analysis will be reported in addition to estimates from the model outlined in Section 6.2 Primary outcome analysis. Any differences between the two and their implications will be discussed in full.

• If missing data cannot be fully explained by the other variables in the dataset, data is likely to be MNAR. In this scenario we will conduct a sensitivity analysis alongside the primary impact analyses.

We will only conduct the above analyses for the primary outcome analysis, as all secondary outcomes analysis, subgroup analysis and further analysis is tentative and exploratory in nature.

There is no universally agreed approach to analyses in the event of item non-completion. In the event that a high proportion of cases would be excluded due to low rates of item non-completion (for example, if most young people miss a small number of items), our approach to missing data will balance considerations around data integrity with maximising statistical power. In this scenario, we would consider using statistical techniques to impute missing items, in line with the YEF analysis guidance (2021a).

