4.1 Overview

The efficacy study is a two-armed parallel RCT, comparing the effectiveness of a dedicated mentoring and case management programme (treatment group) to light-touch young person-led wellbeing and safety support (control group) in reducing children and young people's future engagement in youth violence and offending behaviours. All young people living in the areas of Cardiff, Swansea, Merthyr Tydfil and Caerphilly who are referred into the project, who are 10-17, who meet the eligibility criteria and who consent to be part of the evaluation are randomly allocated to either the treatment or control group on a 1:1 basis.²

Recruitment is taking place on a rolling basis between April 2024 and September 2025. MAC have established various referral routes in partnership with a range of key referral organisations including statutory and non-statutory organisations. These include (but are not limited to):

- Social Services (Children's Services).
- Schools and Pupil Referral Units.
- Youth Services.

.

² Young people are eligible for Cerridwen if they meet all three of the following inclusion criteria: (1) Young people are exhibiting or are at risk of exhibiting violent behaviours, (2) Young people are living in the areas of Cardiff, Swansea, Merthyr Tydfil or Caerphilly, and (3) Young people are willing to engage with and complete Cerridwen. For more detail, please see the evaluation protocol.

- Youth Offending Services.
- Voluntary and Community Sector Organisations.³
- Self-referrals including young people and parents/carers.⁴

Referral sources and the number of eligible and ineligible referrals are monitored and will be reported in the final evaluation report.

Randomisation is conducted at the individual (young person) level, without stratification, in randomly varying block sizes of four, six and eight young people. The randomisation sequence was generated using an online randomisation service (Sealed Envelope).⁵ Team members responsible for analysis were not involved in generating the randomisation sequence. For more information on the design of the randomisation process, please see the evaluation protocol.

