5.1 Overview

The primary objective of the Efficacy Study is to assess the effect of the Media Academy Cymru's (MAC) Cerridwen programme on self-reported offending as measured by the volume score on the Self-Reported Delinquency Scale (Smith & McVie, 2003). A sample size of 592 (296 per group), based on detecting a Minimum Detectable Effect Size (MDES) of 0.20 (equivalent to a 10% difference in proportions), assuming a correlation between baseline and follow-up of 0.5 (Humayun et al., 2019) and using a two-sided alpha of 0.05, would provide 80% power (Figure 2). Our assumptions about the MDES are informed by the YEF guidance (2021a) and previous research. For example, a meta-analysis using a random effects model (d=.21, 95% confidence interval, .07 to .34) of 18 studies, showed that mentoring programmes similar to Cerridwen make a 10-11% difference in relation to offending (Jolliffe & Farrington, 2008). We have also included the pre-post correlation based on values obtained from unpublished data from an RCT using the same outcome measure and in a similar population of adolescents (Humayun et al., 2019).

We have calculated the overall sample size for the trial a priori, in line with YEF guidance (2021a and 2021b). This is presented in the table below. The final sample for the trial will not be finalised until randomisation is complete in October 2025. We will update this table with the final figures once they are known.

These calculations were made with the Powerup! software package (Dong, N. and Maynard, R. A., 2013).

Figure 2: Sample size calculations

		Protocol	Randomisation
Minimum Detectable Ef	fect Size (MDES)	0.20	
	level 1 (participant)	0.5	
Pre-test/ post-test correlations	level 2 (cluster)	N/A	
	level 1 (participant)	N/A	

		Protocol	Randomisation
Intracluster correlations (ICCs)	level 3 (cluster)	N/A	
Alpha		0.05	0.05
Power		0.8	0.8
One-sided or two-sided	One-sided or two-sided?		
	intervention	296	
Number of participants	control	296	
	total	592	

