6.1 Overview

This section presents the analytical approach for the Cerridwen efficacy study.⁹

All analysis will be conducted once delivery comes to an end in April 2025. Analysis will be conducted on an intent-to-treat basis in line with YEF guidance. This means that all participants will be analysed according to their allocation, regardless of whether they received the Cerridwen intervention or not. This provides the most conservative estimate of impact, as this approach evaluates the impact of offering the intervention to those who do and do not comply and helps to fully capture the 'true' benefit (if any) of the intervention (Torgerson and Torgerson, 2008). This approach is particularly relevant for policymakers and commissioners, i.e. those who may roll out an intervention but do not have control over take-up of the intervention across the system.

The analytical approach has been developed a priori and will be conducted in SPSS 25.¹⁰

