6.2 Primary outcome analysis

The primary outcome is the volume of offending at the individual level as measured by the self-reported delinquency scale (SRDS; Smith & McVie, 2003), completed before randomisation and at five-months post randomisation. Young people are asked to report behaviours they have been involved in over the previous five months.

There is considerable debate about best practice when it comes to the analysis of data from RCTs. For example, Twisk et al. (2018) advocate for utilising longitudinal analysis of covariance or a repeated measures analysis without the treatment variable, but with the interaction between treatment and time in the model controlled for. They argue that failure to control for baseline differences in outcomes between the groups can lead to biased treatment estimates. Alternatively, others have cautioned against this approach (Sen, 2013).

Based on our understanding of such literature, our analysis of the impact of the Cerridwen programme on the SRDS volume score will be conducted using a fixed effects analysis of covariance (ANCOVA) model, controlling for baseline SRDS score and site. The ANCOVA analysis will calculate the mean difference in SRDS scores between young people who received support from Cerridwen (the treatment group) and those who received 'light touch' wellbeing

⁹ In line with YEF requirements this plan has been written before all baseline data for the efficacy study has been collected.

¹⁰ IBM Corp. Released 2017. IBM SPSS Statistics for Windows, Version 25.0. Armonk, NY: IBM Corp.

support (the control group), whilst accounting for baseline SRDS score and site. The outputs from this analysis will be used to calculate the Hedges' G effect estimate (described in Section 6.11). We have adjusted for site because Cerridwen, although managed by one central team, is being delivered in three areas (Cardiff, Merthyr Tydfil, Swansea and Caerphilly) by areaspecific case managers who do not work across multiple sites. Adjusting for site will therefore help isolate and understand the influence of location-specific factors (such as geographic variation and staff influence) on the primary outcome.

We will use the following model:

$$Y_i = \beta_0 + \beta_1 Baseline_i + \beta_2 Group_i + \delta Area_k + \varepsilon_i \in N(0, \sigma^2)$$

For i = 1, ..., n young people per area, and k = 1, ..., K Area

Where:

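### The plan has no rule that keeps young people with a T2 score but no usable baseline score in the headline ANCOVA; the cost is a little precision, not bias

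*SAP*

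**What the plan says.** - **Model.** SAP 6.2 fixes an ANCOVA of the T2 SRDS volume score on group, baseline volume score and area. It has no provision for a case whose baseline score is missing.
- **Timing.** The SRDS is "completed before randomisation and at five-months post randomisation" (6.2).
- **Missing baseline data foreseen.** SAP 6.8 names incomplete baseline questionnaires as well as incomplete T2 questionnaires. The volume score is a sum over 19 items (4.3), so blank items can leave it undefined.
- **Below 5% missing.** 6.8 accepts complete cases and takes no other step.
- **Otherwise, for covariates.** "If a covariate is MAR conditional on other covariates, we will conduct multiple imputation (MI". The result is an addition: "Treatment effects from the MI analysis will be reported in addition to estimates from the model outlined in Section 6.2 Primary outcome analysis".
- **Unexplained missingness.** It is taken as likely MNAR and leads to a sensitivity analysis whose form is not given.
- **Blank items.** The last paragraph of 6.8 says imputation of items would be considered if many cases would otherwise be lost. It is not limited to T2.
- **Scope.** 6.8 applies its missing-data steps to the primary outcome only, while 6.3 uses the same ANCOVA with each secondary measure's own baseline.

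**The concern.** Section 6.8 takes a missing baseline covariate through the same mechanism-based route as a missing outcome, but the two differ. A T2 score can be missing for reasons linked to allocation. A baseline score collected before randomisation cannot: its absence is settled before the arm is known, whatever caused it. Whether the mechanism is MAR or MNAR therefore does not matter for protecting the treatment comparison, and inclusion in the headline model need not depend on it.

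The covariate trigger also has no stated test. The logistic models in 6.8 are specified for missing outcomes only.

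What is at stake is the loss from the headline estimate of randomised young people whose outcome is known, in a trial whose realistic analysed sample has already been revised from 592 to 367 (5.1).

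**Working it through.** **Inputs from SAP 4.1 and 5.1.** Allocation is 1:1. Two-sided alpha is 0.05 and power 80%. The correlation is 0.5, so R² = 0.25. The planned analysed sample is 592 for a minimum detectable effect size (MDES) of 0.20; the updated one is 367 for an MDES of 0.25. The share *m* with a T2 score but no baseline score is not given; 2% to 20% is assumed here.

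**Step 1: reproduce the plan's figure.** With MDES = (t₀.₉₇₅ + t₀.₈₀) × √[(1 − R²)/(0.25 N)] and N − 3 degrees of freedom, N = 592 gives 0.1998, which matches the stated 0.20. N = 367 gives 0.254 against the stated 0.25.

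**Step 2: variance of the treatment effect (outcome SD = 1).**
- Cases without a baseline score dropped: 4 × 0.75 / [N(1 − m)].
- All kept, with pooled-mean imputation and an indicator: 4 × (0.75 + 0.25m) / N. Those without a baseline score get no adjustment, so their residual variance is 1 rather than 0.75.

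Power = Φ(effect/SE − 1.96).

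**Step 3: N = 367, effect 0.25.** With nothing missing, SE = √(3/367) = 0.0904 and power is 79.0%.

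| m (assumed) | SE dropped | SE kept | Power dropped | Power kept | Gain (points) |
|---|---|---|---|---|---|
| 2% | 0.0913 | 0.0907 | 78.2% | 78.7% | 0.5 |
| 5% | 0.0928 | 0.0912 | 76.9% | 78.3% | 1.4 |
| 10% | 0.0953 | 0.0919 | 74.6% | 77.6% | 3.0 |
| 20% | 0.1011 | 0.0934 | 69.6% | 76.3% | 6.7 |

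For example, at 10%: dropped, √(3/330.3) = 0.0953; kept, √(3.1/367) = 0.0919.

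**Step 4: check for bias by simulation.** There were 6,000 trials per setting with N = 592, four areas and a true effect of 0.20. The chance of a missing baseline score depended on the score itself.

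| m | Dropped: mean estimate, SE | Kept: mean estimate, SE |
|---|---|---|
| 5% | 0.200, 0.0725 | 0.200, 0.0708 |
| 10% | 0.201, 0.0756 | 0.201, 0.0720 |
| 20% | 0.199, 0.0813 | 0.200, 0.0737 |

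Neither approach is biased even though the missingness is not at random. Only precision differs.

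**The case against.** **The group may be small, and part of it is already covered.** Baseline precedes randomisation, so few randomised young people should lack the questionnaire altogether. Blank items are the likelier source, and the last paragraph of 6.8 may recover those. This stands as a limit on size. It does not remove the point, because that paragraph promises only to consider imputation, and only when many cases would be lost.

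**Exclusion is not stated.** True. It is implied by the model and by the complete-case wording. If multiple imputation is triggered, these young people return in the supplementary estimate, but not in the headline.

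**Multiple imputation is a recognised method, and 6.8 follows the funder's flow chart.** Also true. The objection here is to making it conditional and supplementary for a baseline score, not to the method.

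Stronger readings that a reader might infer, and that the SAP does not support:
- *The headline estimate would be biased.* It would not: missingness fixed before randomisation cannot depend on the arm.
- *The plan breaks its intention-to-treat promise.* The sentence in 6.1, "all participants will be analysed according to their allocation, regardless of whether they received the Cerridwen intervention or not", is about receipt of the intervention, not missing covariates.
- *The whole fall from 79.0% power is recoverable.* It is not. Those without a baseline score still contribute unadjusted outcomes, so the gain is only the last column of the Step 3 table. Also, 367 is already net of attrition in the table in 5.1, and some of this loss may be counted there.
- *A baseline gap would be labelled MNAR and discredit the result.* The stated diagnostic models concern missing outcomes, and the stated consequence is only a sensitivity analysis.

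**Conclusion.** The point holds as a cheap improvement. As written, a young person with a T2 score and no usable baseline score is implicitly absent from the headline ANCOVA, for no reason that validity requires.

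The recoverable power at 367 analysed is about 1.4 points at 5% missing and 3.0 points at 10%. In the branch below 5%, where the plan takes no action, the loss is under about 1.4 points. These figures rest on the SAP's correlation of 0.5, on assumed missing shares, on a linear ANCOVA with a common treatment effect, and on baseline being completed before randomisation as 6.2 states. The argument applies to missing baseline scores only and gives no reassurance about missing T2 scores.

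**What to change.** Add to SAP 6.8:

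> Every randomised young person with a T2 score is included in the 6.2 ANCOVA. A baseline score still missing after any item-level imputation is set to the pooled baseline mean, and a missing-baseline indicator is added. The MAR/MNAR assessment is not applied to baseline scores.

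Use the same rule in the 6.3 ANCOVAs, which otherwise have no committed route for these cases. Keep the existing multiple-imputation bullet for any other covariates added to the model; deleting it would leave them without a rule.

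The cost is one extra model term, a few lines of SAP text and a small departure from the cited funder flow chart, which should be noted. Section 6.2 allows a non-parametric ANCOVA, Tobit or two-part model if the score is skewed or assumptions fail. The check above covers the linear ANCOVA only, so the handling of missing baseline scores should be checked again for whichever model replaces it.

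### The missing-data rules in SAP Section 6.8 infer the mechanism from observed predictors of dropout, which cannot separate MAR from MNAR, and let that inference decide both the sensitivity analysis and the covariates of the primary model

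*SAP*

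**What the plan says.** Section 6.8 sets out how the mechanism will be found: "We will attempt to establish the missing mechanism (i.e. which variables in the data are predictive of non-response) through logistic regression models". Four rules follow, for the primary outcome only.

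- Low missingness: "If the prevalence of missing data is less than 5%, no further action is required as complete case analysis is unlikely to be biased".
- Outcome judged MAR: "If outcomes data is MAR conditional on co-variates, we will include these co-variates in our primary analysis model". No covariates are named, no selection threshold is given, and nothing says that the Section 6.2 estimate will be shown beside the extended model.
- Covariate judged MAR: multiple imputation, reported in addition to the Section 6.2 model.
- Otherwise: "If missing data cannot be fully explained by the other variables in the dataset, data is likely to be MNAR". The consequence is: "In this scenario we will conduct a sensitivity analysis alongside the primary impact analyses". No method, scenario or range is given.

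MCAR is named as a possible finding, but no rule covers it once missingness reaches 5%.

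Section 6.2 fixes the primary model as ANCOVA on baseline SRDS and site, and gives the avoidance of fishing as the reason for fixing it in advance. Section 6.6 adds that sensitivity analysis or imputation will be considered if attrition is high but manageable.

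**The concern.** MAR and MNAR differ in whether missingness still depends on the unseen value once the observed data are taken into account. A regression of missingness on observed variables has no access to that value, so it cannot decide between them. Finding no predictor is what MCAR produces, yet the rule reads it as a sign of MNAR. Finding a predictor does not establish MAR, because dropout driven by T2 offending will usually show up as an association with baseline offending.

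Two decisions hang on this diagnosis: whether any sensitivity analysis for informative dropout is run, and which covariates enter the primary model. At stake is whether the headline effect on offending comes with an adequate check against informative loss. One arm has weekly sessions and the other light-touch support, so it is plausible, though not shown, that the two arms lose different kinds of young people.

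**Working it through.** **1. The plan's own figure.** Section 5.1 gives 592 analysed for an MDES of 0.20, a pre-post correlation of 0.5, two-sided alpha 0.05 and 80% power. Per arm, n = 2(1 − 0.5²)(1.960 + 0.842)²/0.20² = 294.3, so 295 per arm and 590 in total. The t-based formula gives 591, and an MDES of 0.1998 at n = 592. The plan's figure reproduces, so the residual variance factor of 0.75 is used below.

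**2. What the logistic regression can detect.** Simulation, 800 trials per cell.

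- From the SAP: correlation 0.5, true effect −0.20, and N and attrition from the Section 5.1 table. The last row uses the 31% attrition level in Section 6.6, with N = 532 assumed so that about 367 remain (532 × 0.69 = 367).
- Assumed: under MNAR, the odds of dropout double per SD of the T2 score. A predictor means p < 0.05. The model holds baseline, arm and five unrelated covariates.

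| N, missing | MCAR: no predictor | MNAR, both arms: any predictor (baseline) | Bias, SD | MNAR, control arm only: any predictor (baseline) | Bias, SD | 95% CI coverage, control arm only |
|---|---|---|---|---|---|---|
| 412, 10% | 68% | 66% (54%) | 0.007 | 45% (20%) | 0.055 | 91% |
| 673, 12% | 69% | 89% (83%) | 0.003 | 53% (31%) | 0.062 | 85% |
| 448, 21% | 71% | 85% (79%) | 0.002 | 50% (32%) | 0.106 | 77% |
| 532, 31% | 68% | 95% (92%) | 0.012 | 54% (37%) | 0.152 | 61% |

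The MCAR column is chance: with seven predictors, 0.95⁷ = 0.70. On the predictor reading, about 70% of truly MCAR trials would be called likely MNAR, and the other 30% would gain a chance covariate. When dropout depended only on the part of the T2 score that baseline does not predict (MNAR by definition), a predictor appeared in 29-32% of trials, against 29-33% under MCAR. The regression did not tell the two apart.

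**3. Size of the bias with no true effect.** 448 randomised, about 19% missing. (The table row for 448 states 21%, but 367/448 implies 18%.) Negative means apparent benefit. Ranges cover slightly different ways of writing the dropout model.

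| Informative dropout | Bias, SD | False positives |
|---|---|---|
| Equal in both arms (log-odds 0.7 or 1.0 per SD of T2) | at most 0.007 | about 5% |
| Modest arm difference (0.7 against 0.3) | −0.05 to −0.06 | 8.5% for −0.05 |
| Mainly treatment arm (1.0 against 0.2 or 0) | −0.09 to −0.14 | 18-35% |
| Mainly control arm (arms swapped) | +0.10 | not tabulated |

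In the mainly-treatment-arm runs, baseline SRDS predicted dropout in 43-63% of trials, which the predictor reading would label MAR.

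**4. Check by hand.** Analysed n = 448 × 0.81 ≈ 363, so SE = √(4 × 0.75/363) = 0.091. The false-positive rate is Φ(−1.96 + b/SE) + Φ(−1.96 − b/SE). For b = 0.05, 0.09 and 0.14 this gives 8.5%, 17% and 34%, in line with the simulated rates. In closed form, if one arm loses a fraction a and its dropouts score δ SD worse than predicted, the bias is a × δ: 0.21 × 0.5 = 0.105 SD. That is 42% of an MDES of 0.25, or 53% of 0.20.

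**5. The model change.** Section 6.2 names two adjustment terms, baseline and site. The MAR rule in Section 6.8 adds whichever covariates turn out to predict dropout. Of the four rules, only the imputation rule promises both results.

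**The case against.** - *The sensitivity analysis.* A reader might infer that the check is switched off exactly when it is needed. The SAP does not go that far. Its trigger is that missingness cannot be fully explained, and no logistic model fully explains dropout, so on a literal reading some sensitivity analysis would nearly always run. The p < 0.05 threshold used above is not in the SAP, and the four rules are not said to exclude one another. What stands is that the SAP's own gloss on the mechanism supports the predictor reading, the two readings lead to opposite actions, and neither specifies an analysis.
- *The report.* A reader might also infer that nothing reported would reveal a problem. That is not so. Sections 6.6 to 6.8 provide for differential attrition, a table of T2 completers and the pattern of missingness. These can give warning signs, though they do not estimate or correct the bias.
- *Intent to treat.* It is tempting to see a conflict with Section 6.1, where "all participants will be analysed according to their allocation". That sentence goes on to deal with whether the programme was received. It concerns non-compliance, not missing T2 scores.
- *Complete cases.* If the outcome is MAR given the covariates in the model, complete-case ANCOVA is unbiased, and imputing from the same covariates adds little. That is accepted, so outcome imputation is offered below only as a secondary analysis.
- *The model change.* It is a stated contingency, and adding baseline covariates to a randomised comparison is a mild departure. What stands is that the covariates are unnamed and the Section 6.2 estimate could be displaced.
- *Funder guidance.* The rules follow a funder flow chart that is not at hand and may hold more detail. That would not make the stated inference valid.
- *MCAR called MNAR.* This errs on the safe side numerically. The harm is a wrong statement about bias and an unspecified extra analysis.

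**Conclusion.** The rule is wrong as written. The mechanism cannot be read from predictors of non-response, MCAR above 5% has no correct branch, and the diagnosis should govern neither the sensitivity analysis nor the primary model.

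The consequence for the estimate is conditional. At about 19% missing, the complete-case ANCOVA bias runs from near zero, through about 0.05 SD, to about 0.09-0.14 SD in either direction, depending on how far informative dropout differs between arms. Nothing in the SAP shows which case will apply. The upper end needs dropout that depends strongly on the T2 score in essentially one arm, and it is not a forecast. The labelling percentages depend on the assumed odds ratios and on p < 0.05 as the test of a predictor. That the mechanism cannot be identified depends on none of these assumptions.

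**What to change.** Replace the decision rules in Section 6.8 with the following.

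1. The Section 6.2 model stays the primary analysis whatever the missingness models show.
2. If more than 5% of T2 SRDS scores are missing, always report a delta-adjusted or tipping-point sensitivity analysis, with delta varied separately by arm (for example 0 to 0.5 SD).
3. Any covariate-extended MAR model, or multiple imputation of the outcome by arm using baseline SRDS, area, age, sex and ethnicity, is reported as secondary to the Section 6.2 estimate. Sessions attended should not be an auxiliary variable unless a control-arm counterpart is recorded, because Section 6.5 describes session data for Cerridwen participants only.
4. The logistic regressions are used only to describe who dropped out.

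The cost is SAP wording and one extra sensitivity table. No new data are needed and the sample size is unaffected.
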